### Cardiac toxicity

The incidence of cardiac AEs is <1%, but a wide range of toxicities including myocarditis, pericarditis, arrhythmias, cardiomyopathy and impaired ventricular function have been reported after treatment with ipilimumab, pembrolizumab and nivolumab [72–75]. However, the incidence of cardiac toxicity is higher with the combination of ipilimumab and nivolumab (0.27%) compared with nivolumab alone (0.06%). Early consultation with a cardiologist is recommended [V, B]. High-dose corticosteroids have been used successfully to treat cardiac side-effects and should be instituted rapidly if checkpoint inhibitor induced cardiac AEs are suspected. Escalation to other immunosuppressive drugs, such as infliximab, MMF and ATG, may be necessary if symptoms do not promptly respond to steroids [V, B].

### Rheumatological toxicity

Mild or moderate myalgias and arthralgias occur in 2%–12% of patients and are more common with anti-PD-1 agents [76]. Vasculitis, polymyositis, myositis and temporal arteritis have also been described [73]. For mild or moderate symptoms, analgesia with paracetamol and/or NSAIDs is recommended [V, B]. In addition, moderate symptoms may respond to prednisolone at a dose of 10–20 mg/day or equivalent. Severe symptoms should prompt consultation with a rheumatologist and consideration of the use of high-dose corticosteroids and TNF $\alpha$ -blocking agents [V, B] (see Figure 13).

### Renal toxicity

Renal dysfunction is rare with ipilimumab and with anti-PD-1 therapies, occurring in <1% of treated patients [77]. The incidence is much higher with combination of ipilimumab plus nivolumab, reaching 4.9%, with 1.7% of grade 3 to 4 toxicity. Similarly, sequential therapy with ipilimumab followed by nivolumab is associated with a high incidence of 5.1%, of which 2.2% of cases developed grade 3 to 4 nephritis [78]. Serum sodium, potassium, creatinine and urea should be measured before every infusion of checkpoint inhibitor and derangement of renal function managed initially by stopping nephrotoxic drugs (including over the counter medications), ruling out infection, urinary tract obstruction and correcting hypovolaemia. Checkpoint inhibitor therapy should be withheld in the event of significant renal dysfunction and consideration given to the use of systemic corticosteroid therapy [0.5–2 mg (methyl)prednisolone or equivalent] [V, B]. In the event of severe renal dysfunction, a nephrologist should be consulted. Renal biopsy may be used to clarify a difficult differential diagnosis [V, B]. In one series of patients who were biopsied after developing acute kidney injury while on ICPis an acute tubulo-interstitial nephritis with lymphocytic infiltration was the most frequent finding [79]. Recently, a severe case of antineutrophil cytoplasmic antibody-associated rapid progressive glomerulonephritis was described in a patient with thymic epithelial carcinoma on pembrolizumab treatment [80]. In keeping with pathology described in other organs, granulomatous changes were seen in about a quarter of patients and one had thrombotic microangiopathy (see Figure 14).

### Ocular toxicities

irAEs of the eye are rare and occur in <1% of patients treated with ICPis [81]. These AEs can be divided into ocular inflammation, such as peripheral ulcerative keratitis, uveitis and Vogt–Koyanagi–Harada syndrome, orbital inflammation, including thyroid-associated orbitopathy and idiopathic orbital inflammation (scleritis, myositis, neuritis, dacryadenitis) and retinal and choroidal disease (choroidal neovascularisation and melanoma-associated retinopathy). Treatment of these rare toxicities depends on their severity, with topical corticosteroids in the case of episcleritis and anterior uveitis, and systemic corticosteroids in the case of severe ocular inflammation and orbital inflammation. Intravitreal anti-vascular endothelial growth factor (VEGF) is indicated for choroidal neovascularisation.

# Clinical Practice Guidelines

Annals of Oncology

## Haematological toxicities

Immune-related haematological AEs have rarely been described in patients treated with ICPi and do seem to occur. So far, lethal aplastic anaemia, autoimmune haemolytic anaemia and immune thrombocytopenic purpura have been described [82–84]. The optimal treatment of these often severe AEs is unknown. Initiation of high-dose corticosteroids and other immunosuppressive drugs should be carried out in close collaboration with a haematologist.

[figure not shown]
## Allograft rejection

The limited literature suggests that ipilimumab as a single agent may be administered without necessarily causing rejection of cardiac, renal and liver allografts. However, several recent case reports have documented the risk of acute allograft rejection after anti-PD-1 therapy [85]. As such, this very significant risk must be

considered in discussing systemic therapy options in patients that might potentially benefit from anti-PD-1 therapy but who have allografted organs.

[figure not shown]
## Methodology

These Clinical Practice Guidelines were developed in accordance with the ESMO standard operating procedures for Clinical Practice Guidelines development [www.esmo.org/Guidelines/ESMO-Guidelines-Methodology](http://www.esmo.org/Guidelines/ESMO-Guidelines-Methodology). The relevant literature has been selected by the expert authors. A summary of recommendations is shown in Table 2. Levels of evidence and grades of recommendation have been applied using the system shown in Table 3. Statements without grading were considered justified standard clinical practice by the experts and the ESMO Faculty. This manuscript has been subjected to an anonymous peer review process.

**Figure 10.** ICPi-related toxicity: management of suspected peripheral neurological toxicity.

ADL, activities of daily living; CVA, cerebrovascular accident; HIV, human immunodeficiency virus; ICPi, immune checkpoint inhibitor; i.v. intravenous; MRA, magnetic resonance angiogram; MRI, magnetic resonance imaging; NCS/EMG, nerve conduction studies/electromyography; PJP, Pneumocystis jiroveci pneumonia; TSH, thyroid-stimulating hormone.

[figure not shown]
**Figure 11.** ICPi-related toxicity: management of suspected peripheral neurological toxicity.

AChR, acetylcholine receptor; EMG, electromyography; GBS, Guillain-Barré syndrome; ICPi, immune checkpoint inhibitor; i.v., intravenous; IVIG, intravenous immunoglobulin; MuSK, muscle specific kinase; tds, three times a day; WBC, white blood cell.

[figure not shown]
Suspected syndrome	Suggested Investigations	Management approach

Aseptic meningitis: Exclusion of infective causes paramount
 
Headache, photophobia, neck stiffness with fever or may be afebrile, vomiting; normal cognition/cerebral function (distinguishes from encephalitis)
	
Lumbar puncture- M/C/S (normal Gram stain, WBCs < 500/<math>\mu</math>L, normal glucose), PCR for HSV, cytology
 
CNS imaging to exclude brain metastases and leptomeningeal disease
	
Exclude bacterial and ideally viral infections prior to high-dose steroids
 
Oral prednisolone 0.5-1 mg/kg or i.v. (methyl)prednisolone 1-2 mg/kg if very unwell
 
Consider concurrent empiric antiviral (i.v. acyclovir) and antibacterial therapy


Encephalitis: Exclusion of infective and metabolic causes paramount
 
Confusion or altered behaviour, headaches, alteration in Glasgow Coma Scale, motor or sensory deficits, speech abnormality, may or may not be febrile
	
Lumbar puncture- M/C/S (normal Gram stain, WBCs usually < 250/mm^3 with lymphocyte predominance, elevated protein but < 150 mg/dL, usually normal glucose but can be elevated), PCR for HSV & consider viral culture, cytology
 
CNS imaging
 
Consider viral serology
	
As above for aseptic meningitis
 
Suggest concurrent i.v. acyclovir until PCR result obtained

Transverse myelitis: Acute or subacute neurological signs/symptoms of motor/sensory/autonomic origin; most have sensory level; often bilateral symptoms
	
MRI brain and spine
 
Lumbar puncture – may be normal but lymphocytosis, elevated protein may be noted, oligoclonal bands not usually present, cytology
 
Serum B12/HIV/syphilis/ANA/anti-Ro and anti-La Abs, TSH, anti-aquaporin-4 IgG
	
(Methyl)prednisolone 2 mg/kg (or consider 1 g/day)
 
Neurology consultation
 
Plasmapheresis may be required if non-steroid responsive

Other syndromes reported:
 
Neurosarcoidosis, Posterior Reversible Leucoencephalopathy Syndrome (PRES), Vogt-Harada-Koyanagi syndrome, Neurosarcoidosis, demyelination, vasculitic encephalopathy, generalised seizures
		

**Figure 12.** ICPi-related toxicity: management of suspected central neurological toxicity.

Abs, antibodies; ANA, antinuclear antibody; CNS, central nervous system; HIV, human immunodeficiency virus; HSV, Herpes simplex virus; ICPi, immune checkpoint inhibitor; IgG, immunoglobulin G; i.v., intravenous; M/C/S, microscopy, culture and susceptibility; MRI, magnetic resonance imaging; PCR, polymerase chain reaction; TSH, thyroid-stimulating hormone; WBCs, white blood cells.

**Figure 13.** ICPI-related toxicity: management of arthralgia.

ADL, activities of daily living; AE, adverse event; DDx, differential diagnosis; ICPI, immune checkpoint inhibitor; MRI, magnetic resonance imaging; TNF $\alpha$ , tumour necrosis factor alpha; US, ultrasound.

**Figure 14.** ICPi-related toxicity: management of nephritis.

Renal injury occurs in around 1%–4% of patients treated with ICPi, usually in a pattern of acute tubulo-interstitial nephritis with a lymphocytic infiltrate [79]. Attention needs to be paid to the patient's baseline creatinine, not just abnormal results per biochemistry ULN. Confounding diagnoses include dehydration, recent i.v. contrast, urinary tract infection, medications, hypotension, or hypertension. Early consideration for renal biopsy is helpful which may negate the need for steroids and determine whether renal deterioration is related to ICPis or other pathology. Oliguria should prompt inpatient admission for careful fluid balance and plan for access to renal replacement therapy. Steroid wean: begin to wean once creatinine G1; G2 severity episode—wean steroids over 2–4 weeks; G3/4 episode—wean over  $\geq$  4 weeks. If on steroids for > 4 weeks—PJP prophylaxis, calcium/vitamin D supplementation, gastric protection and check afternoon glucose for hyperglycaemia. \*GN screen: ANA, complement C3, C4, ANCA, anti-GBM, hepatitis B and C, HIV, immunoglobulins and protein electrophoresis. ANA, antinuclear antibody; ANCA, anti-neutrophil cytoplasmic antibody; GBM, glomerular basement membrane; GN, glomerulonephritis; HIV, human immunodeficiency virus; ICPi, immune checkpoint inhibitor; irAE, immune-related adverse event; i.v., intravenous; K, potassium; PJP, Pneumocystis jiroveci pneumonia; ULN, upper limit of normal; UPCR, urine protein to creatinine ratio.

**Table 2. Summary of recommendations for immune-related toxicities****Immune-related skin toxicity**

- For grade 1–2 skin AEs, continue (at least 1 week) with ICPIs. Start topical emollients, antihistamines in the case of pruritus and/or topical (mild strength) corticosteroid creams. Reinitiate ICPI when  $\leq$  grade 1.
- For grade 3 skin AEs, interrupt ICPI and start immediate treatment with topical emollients, antihistamines and high strength corticosteroid creams [II, B].
- For grade 4 skin AEs, discontinue ICPI (permanently), consider admitting patient and always consult dermatologist immediately. Start i.v. corticosteroids [1–2 mg/kg (methyl)prednisolone] and taper based on response of AE [II, B].

**Immune-related endocrinopathies**

- In symptomatic hyperthyroidism patients, usually grade 1 or 2, interrupt ICPI, start beta-blocker therapy (propranolol or atenolol/metoprolol). Restart ICPI when asymptomatic [IV–V, B].
- In the case of hypothyroidism, rarely > grade 2, start HRT depending on the severity (50–100  $\mu$ g/day). Increase the dose until TSH is normal. In the case of inflammation of the thyroid gland, start prednisone orally 1 mg/kg. Taper based on recovery of clinical symptoms. Consider interruption of ICPI treatment when symptomatic [IV–V, B].
- In the case of hypophysitis (rarely > grade 2), when headache, diplopia or other neurological symptoms are present, start (methyl)prednisolone 1 mg/kg orally and taper over 2–4 weeks. Start HRT depending on the affected hormonal axis (levothyroxine, hydrocortisol, testosterone) [IV, B].
- In patients with type I DM grade 3 to 4 [ketoacidotic (sub)coma], admit to hospital immediately and start treatment of newly onset type I DM [I, A]. Role of corticosteroids in preventing complete loss of insulin producing cells is unknown and not recommended.

**Immune-related hepatotoxicity**

- For grade 2 hepatitis, withhold ICPI and monitor AST/ALT levels closely (1–2 times/week). When no improvement over 1 week, start (methyl)prednisolone (0.5–1 mg/kg). Taper over several weeks under close monitoring of AST/ALT and bilirubin [IV–V, B].
- For grade 3 hepatitis, discontinue ICPI and immediately start with (methyl)prednisolone 1–2 mg/kg. When no improvement in 2–3 days, add MMF (1000 mg 3 x daily). Taper immunosuppression over 4–6 weeks under close monitoring of AST/ALT and bilirubin [IV–V, B].
- For grade 4 hepatitis, permanently discontinue ICPI, admit patient to the hospital and initiate (methyl)prednisolone 2 mg/kg i.v. Add MMF if no improvement is observed within 2–3 days. Consult hepatologist if no improvement under double immunosuppression. Other immunosuppressive drugs to consider are ATG and tacrolimus. Consult or refer patient to an experienced centre. Taper over 6 weeks under close monitoring of liver tests [IV–V, B].

**Gastrointestinal hepatotoxicity**

- In patients with non-severe diarrhoea (grade 1), ICPI can be continued. Treatment with antidiarrhoeal medication (e.g. loperamide) should be prescribed [IV–V, B].
- In grade 2 diarrhoea, ICPI should be interrupted and the patient should start with corticosteroids depending on the severity and other symptoms (either budesonide or oral corticosteroids 1 mg/kg). In the case of no improvement within 3–5 days, colonoscopy should be carried out and, in the case of colitis, infliximab 5 mg/kg should be administered [IV–V, B].
- In patients with severe diarrhoea (grade 3 to 4), permanently discontinue ICPI. Admit patient to the hospital and initiate (methyl)prednisolone 2 mg/kg i.v. Add MMF if improvement is observed within 2–3 days. Consult a hepatologist if no improvement under double immunosuppression. Other immunosuppressive drugs to consider are ATG and tacrolimus. Consult or refer patient to an experienced centre. Taper over 6 weeks under close monitoring of liver tests [IV–V, B].

**Immune-related pneumonitis**

- In grade 1 and 2 pneumonitis, interrupt ICPI therapy, try to rule out infection and start with prednisolone 1–2 mg/kg orally. Taper over 4–6 weeks [IV–V, B].
- In grade 3 and 4 pneumonitis, discontinue ICPI permanently, admit the patient to the hospital, even ICU if necessary and immediately start high-dose (methyl)prednisolone 2–4 mg/kg i.v. Add infliximab, MMF or cyclophosphamide in the case of deterioration under steroids. Taper over a period of 4–6 weeks [IV–V, B].

**Neurological toxicity**

- In the case of mild neurological AEs, withhold ICPI and perform work-up (MRI scan, lumbar puncture) to define nature of neurotoxicity. In the case of deterioration or severe neurological symptoms, admit the patient and start (methyl)prednisolone 1–2 mg/kg orally or i.v. In the case of Guillain-Barré or myasthenia-like symptoms, consider adding plasmapheresis or i.v. Ig [V, B].

**Cardiac toxicity**

- When a myocarditis is suspected, admit the patient and immediately start high-dose (methyl)prednisolone (1–2 mg/kg). In the case of deterioration, consider adding another immunosuppressive drug (MMF or tacrolimus) [V, B].

**Rheumatological toxicity**

- For mild arthralgia, start NSAIDs, and in the case of no improvement, consider low dose steroids (10–20 mg prednisolone). In the case of severe polyarthritis, refer patient to or consult a rheumatologist and start prednisolone 1 mg/kg. Sometimes infliximab or another anti-TNF $\alpha$  drug is required for improvement of arthritis [V, B].

**Renal toxicity**

- In case of nephritis, rule out other causes of renal failure first. Interrupt or permanently discontinue ICPI depending on the severity of the renal insufficiency. Stop other nephrotoxic drugs. Start (methyl)prednisolone 1–2 mg/kg. Consider renal biopsy to confirm diagnosis [V, B].

AE, adverse event; ALT, alanine transaminase; AST, aspartate transaminase; ATG, anti-thymocyte globulin; DM, diabetes mellitus; HRT, hormone replacement therapy; ICPI, immune checkpoint inhibitor; ICU, intensive care unit; Ig, immunoglobulin; i.v. intravenous; MMF, mycophenolate mofetil; MRI, magnetic resonance imaging; NSAIDs, nonsteroidal anti-inflammatory drugs; TNF $\alpha$ , tumour necrosis factor alpha; TSH, thyroid-stimulating hormone.

# Clinical Practice Guidelines

Annals of Oncology

**Table 3. Levels of evidence and grades of recommendation (adapted from the Infectious Diseases Society of America–United States Public Health Service Grading Systema)**

Levels of evidence	
I	Evidence from at least one large randomised, controlled trial of good methodological quality (low potential for bias) or meta-analyses of well-conducted randomised trials without heterogeneity
II	Small randomised trials or large randomised trials with a suspicion of bias (lower methodological quality) or meta-analyses of such trials or of trials demonstrated heterogeneity
III	Prospective cohort studies
IV	Retrospective cohort studies or case–control studies
V	Studies without control group, case reports, expert opinions

Grades of recommendation	
A	Strong evidence for efficacy with a substantial clinical benefit, strongly recommended
B	Strong or moderate evidence for efficacy but with a limited clinical benefit, generally recommended
C	Insufficient evidence for efficacy or benefit does not outweigh the risk or the disadvantages (adverse events, costs, ...) optional
D	Moderate evidence against efficacy or for adverse outcome, generally not recommended
E	Strong evidence against efficacy or for adverse outcome, never recommended

aBy permission of the Infectious Diseases Society of America [88].

## Disclosure

FC has reported being a board member of Merck Sharpe & Dohme and Bristol-Myers Squibb and honoraria from Bristol-Myers Squibb; CR has reported consultancy for Roche, Bristol-Myers Squibb, Amgen, Merck Sharpe & Dohme, Novartis and Merck; KK has reported lecture honoraria and/or consultancy from AstraZeneca, Bristol-Myers Squibb, Boehringer Ingelheim, Eli Lilly, Merck KGaA, Merck Sharpe & Dohme, Novartis, Pfizer, Roche and Roche Diagnostics; JL has reported honoraria and research grants from Bristol-Myers Squibb, Merck Sharpe & Dohme, Novartis, Pfizer, Eisai, GlaxoSmithKline, Kymab, Roche/Genentech, Secarna, Fabre and EUSA Pharma; JH, SP and KJ has reported honoraria from Amgen, Merck, MSD, Helsinn, Tesaro and Hexal and being a member of the advisory board of Merck, MSD, Helsinn and Tesaro.

## APPENDIX 10: CYTOKINE RELEASE SYNDROME GRADING AND TREATMENT GUIDELINES

The following guidelines have been adapted from ([Lee 2014](#)). Please refer to the full publication for further details. These may be supplemented by discussions with the Sponsor's medical monitor as well as institutional guidelines on management of CRS.

**Table 16: Cytokine Release Syndrome Grading and Treatment Guidelines**

Grade/Toxicity	Treatment
Grade 1  Symptoms are not life threatening and require symptomatic treatment only, eg, fever, nausea, fatigue, headache, myalgias, malaise	Vigilant supportive care Assess for infection Treat fever and neutropenia if present, monitor fluid balance, antipyretics, analgesics as needed
Grade 2  Symptoms require and respond to moderate intervention  Oxygen requirement <40% or Hypotension responsive to fluids or low dose of one vasopressor or Grade 2 organ toxicity 	Extensive comorbidities or older age: Vigilant supportive care Tocilizumab  +/- corticosteroids  No Extensive comorbidities or older age: Vigilant supportive care (Monitor cardiac and other organ function closely)
Grade 3  Symptoms require and respond to aggressive intervention  Oxygen requirement ≥40% or Hypotension requiring high dose  or multiple vasopressors or Grade 3 organ toxicity or grade 4 transaminitis	Vigilant supportive care Tocilizumab +/- corticosteroids
Grade 4  Life-threatening symptoms Requirement for ventilator support or Grade 4 organ toxicity (excluding transaminitis)	Vigilant supportive care Tocilizumab +/- corticosteroids
Grade 5  Death	NA

 Tocilizumab 4 mg/kg over 1 hour. Repeat dose if no improvement in 24-48 hours

 Methylprednisolone 2 mg/kg/day IV; dexamethasone 0.5 mg/kg (10 mg/dose) IV every 6 hours

 As determined by CTCAE Ver 4.03

 Refer to [Table 17](#)

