#### 4.6 Justification for Dose

The MABEL approach was used to determine a safe first in human starting dose for FPT155. This approach was used because FPT155 functions through 2 key T cell regulators or modulators, including co-stimulation of CD28 on T cells after T cell receptor engagement, and blocking CTLA-4 from competing for endogenous CD80.

The FPT155 starting dose was based on the established guidelines for MABEL dosing and relevant literature ([Saber 2016](#)). Based on these guidelines, RO and PA between 20-80% are appropriate for selecting starting doses. For FPT155, assessments of RO and PA through both CTLA-4 and CD28 were considered. To project the human dose based on  $C_{max}$ , assumptions of a plasma volume of distribution of central compartment of 2800 mL and a 70 kg average patient weight were used in calculating the percent RO and PA.

Integrating the assessments of RO and PA through both CTLA-4 and CD28, a starting dose of 0.07 mg was selected. Among the PA assays examined, CTLA-4 ELISA was thought to be both biologically relevant and sensitive. Using this ELISA assay, 50% PA leads to a predicted starting dose, when rounded down, of 0.07 mg. Several PA assays for CD28 activity were considered, however these assays were either thought to be not biologically relevant or predicted a much higher starting dose.

The Sponsor has selected a Q3W dosing interval. Although the half-life of FPT155 in patients is predicted to be less than 10 days, preclinical evidence suggests that the total exposure, not  $C_{trough}$ , may be an important driver of efficacy. A Q3W interval between doses was thought to be appropriate because no target trough concentration has been identified to achieve between dose interval from nonclinical efficacy studies.

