### **6.9.5 Management of CRS**

Refer to [Appendix 10](#) for specific guidelines for grading and management of CRS.

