## **8.4      Adverse Events and Serious Adverse Events**

The definitions of an AE or SAE can be found in [Appendix 2](#).

Assessment of AEs will follow the guidelines provided in the NCI CTCAE version 4.03.

Abnormal laboratory results that lead to a change in patient treatment management (e.g., dose delay, requirement for additional medication or monitoring) are considered clinically significant for the purposes of this study and will be recorded on the AE page of the eCRF.

AEs will be reported by the patient (or, when appropriate, by a caregiver, surrogate, or the patient's legally authorized representative).

The investigator and any designees are responsible for detecting, documenting, and recording events that meet the definition of an AE or SAE and remain responsible for following up AEs to resolution.

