### 3. Recording an AE and/or SAE

AE and SAE Recording

The investigator will record all available relevant AE/SAE information in the CRF and send it to the sponsor or designee within 24 hours of becoming aware of the event.
 
There may be instances when copies of medical records for certain cases are requested by the Sponsor. In this case, all patient identifiers, with the exception of the patient number, will be redacted on the copies of the medical records before submission.
 
The investigator will attempt to establish a diagnosis of the event based on signs, symptoms, and/or other clinical information. Whenever possible, the diagnosis (not the individual signs/symptoms) will be documented as the AE/SAE.

Assessment of Intensity

Investigators need to assess the severity of AEs according to the guidelines provided in NCI-CTCAE, version 4.03. CTCAE v 4.03 Severity Grades are:
 
Grade 1: Mild; asymptomatic or mild symptoms; clinical or diagnostic observations only; intervention not indicated; mild AE
 
Grade 2: Moderate; minimal, local or non-invasive intervention indicated; limiting age-appropriate instrumental activities of daily living; moderate AE
 
Grade 3: Severe or medically significant but non-immediately life-threatening; hospitalization or prolongation of hospitalization indicated; disabling; limiting self-care activities of daily living; severe AE
 
Grade 4: Life-threatening consequences; urgent intervention indicated
 
Grade 5: Fatal AE
 
If the AE is not specified in the CTCAE or the study protocol, the grading of severity will be assessed as mild (Grade 1), moderate (Grade 2), severe (Grade 3), life-threatening (Grade 4), or death due to the AE (Grade 5) using the following definitions:
 
Mild: The patient is aware of the event or symptom, but the event or symptom is easily tolerated.
 
Moderate: The patient experiences sufficient discomfort to interfere with or reduce his or her usual level of activity.
 
Severe: Significant impairment of functioning; the patient is unable to carry out usual activities.
 
Very severe (life-threatening): The patient's life is at risk from the event.

Assessment of Causality

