6.3.1.2 Adverse Event Severity

Adverse events will be graded for severity by the investigators using the National Cancer Institute Common Toxicity Criteria for Adverse Events (NCI-CTCAE) Version 4.03. The severity grade of events for which the investigator did not record severity will be categorized as “missing” for tabular summaries and data listings.

- Grade 1: Mild; asymptomatic or mild symptoms; clinical or diagnostic observations only; intervention not indicated; mild AE
- Grade 2: Moderate; minimal, local or non-invasive intervention indicated; limiting age-appropriate instrumental activities of daily living; moderate AE
- Grade 3: Severe or medically significant but non-immediately life-threatening; hospitalization or prolongation of hospitalization indicated; disabling; limiting self-care activities of daily living; severe AE
- Grade 4: Life-threatening consequences; urgent intervention indicated
- Grade 5: Fatal AE

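### Table 16 prints two dexamethasone amounts for cytokine release syndrome without saying how they relate: 35 mg or 10 mg per dose at 70 kg

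*Protocol*

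**What the plan says.** **Steroid dose.** Table 16 offers corticosteroids as an optional addition to tocilizumab for CRS of Grades 2 to 4; at Grade 2 this is for patients who are older or have extensive comorbidities. Footnote 2 gives two regimens. One is "Methylprednisolone 2 mg/kg/day IV" and the other is "dexamethasone 0.5 mg/kg (10 mg/dose) IV every 6 hours". The footnote says nothing more about how the weight-based and fixed amounts relate. The introduction to Appendix 10 says the guidance is adapted from a publication, refers sites to it, and allows supplementing by the medical monitor and by institutional guidelines.

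**Grading.** Protocol 6.9.5 refers to Appendix 10 "for specific guidelines for grading and management of CRS". Table 16 defines its own CRS Grades 1 to 5 and takes only the organ-toxicity component from CTCAE 4.03 (footnote 3). For adverse events in general, protocol 8.4 says "Assessment of AEs will follow the guidelines provided in the NCI CTCAE version 4.03". Protocol Table 12 sets the same scale, and SAP 6.3.1.2 says "Adverse events will be graded for severity by the investigators using the National Cancer Institute Common Toxicity Criteria for Adverse Events", version 4.03. None of these three places makes an exception for CRS. The DLT list in 4.1.1.3 counts Grade 3-4 non-haematological toxicity, with exceptions, and names no scale. Table 9 mentions CRS in its Grade 2 row, with a footnote to 6.9.5 and Appendix 10.

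**The concern.** A weight-based amount followed by a fixed amount in brackets is naturally read as the same dose stated twice. Here the two cannot be the same dose for any adult. Two sites treating the same patient from the same line could give amounts several-fold apart and each believe it had followed the protocol. The instruction is meant for moderate to life-threatening CRS, when there may be little time to consult another source. Protocol 2.4 gives CRS particular attention because of the experience with an anti-CD28 superagonist antibody. Two monotherapy dose levels (840 and 1260 mg) and the pembrolizumab combination lie beyond the experience reported in the protocol.

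The grading question is smaller. Two scales can apply to one CRS event, and the documents do not rank them where a grade drives a decision or a table.

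**Working it through.** **Inputs**
- Weight-based amount 0.5 mg/kg, fixed amount 10 mg per dose, every 6 hours (four doses a day): Table 16, footnote 2.
- Adults only: inclusion criterion 1.01.
- Reference weight 70 kg: section 4.6, "a 70 kg average patient weight were used in calculating the percent RO and PA". It was set for the starting-dose calculation and is used here only as the protocol's own adult figure. The 50 to 90 kg range is an assumption.

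**Reading A: as printed, both amounts per dose**
- Weight at which they agree: 10 / 0.5 = 20 kg.
- At 70 kg: 0.5 x 70 = 35 mg against 10 mg; 35 / 10 = 3.5. Per day: 35 x 4 = 140 mg against 10 x 4 = 40 mg.
- At 50 kg: 25 mg against 10 mg, 2.5-fold.
- At 90 kg: 45 mg against 10 mg, 4.5-fold.

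The bracketed 10 mg is therefore not reproduced from 0.5 mg/kg at any plausible adult weight.

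**Reading B: 0.5 mg/kg is a daily total in four parts**
- At 70 kg: 35 / 4 = 8.75 mg per dose, or 0.875 of 10 mg.
- Weight at which they agree: 10 x 4 / 0.5 = 80 kg.

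This is close to 10 mg near average adult weights. It needs a per-day unit, which the footnote prints for methylprednisolone and not for dexamethasone.

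**Reading C: 10 mg is a ceiling on each dose**
- Dose = the smaller of 0.5 x weight and 10 mg, so the ceiling applies above 20 kg.

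There is then no conflict, but the footnote has no word marking a maximum. The weight-based figure would also have no effect for any patient above 20 kg.

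**Grading, passages side by side**
- Table 16 classes a grade 4 transaminitis, graded by CTCAE 4.03, as CRS Grade 3, and excludes transaminitis from CRS Grade 4.
- Table 9 lets a first Grade 3 event that recovers within 14 days resume treatment, but discontinues permanently for any Grade 4.

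One patient can therefore fit two rows of Table 9, depending on whether the CRS grade or the CTCAE grade of the liver finding is used. A worst-grade table under the SAP could likewise show 3 or 4. Nothing here affects sample size, power or confidence level.

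**The case against.** **On the dose.** An unlabelled bracket is an ambiguity, and a reader might go further and infer that Table 16 flatly contradicts itself. The documents do not establish that: under a ceiling reading the conflict disappears, and the 3.5-fold figure belongs to Reading A alone. Appendix 10 also points to its source, and steroids are optional in Table 16. All of this stands. What remains is that the protocol states neither the ceiling nor the daily-total reading, and the referral elsewhere does not explain the line as printed. The origin of the 70 kg figure matters little, because no plausible adult weight makes the two amounts agree under Reading A.

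**On grading.** Three stronger inferences are tempting and do not hold.
- That a separate CRS scale is itself an error. It is deliberate: 6.9.5 assigns CRS grading to Appendix 10, and Appendix 2 foresees events whose grading the protocol specifies.
- That Table 9 is silent on the scale for CRS. Its footnote b leads to 6.9.5 and Appendix 10.
- That regrading CRS from 2 to 3 changes the 3+3 count. This would set Table 16's Grade 2 wording, "Hypotension responsive to fluids or low dose of one vasopressor", against the general Grade 3 heading in Appendix 2, "Severe or medically significant but non-immediately life-threatening; hospitalization or prolongation of hospitalization indicated". That heading is generic, and the general Grade 2 heading is moderate, as is the intervention in Table 16's Grade 2. How CTCAE 4.03 grades CRS itself is not in the documents, so the regrade is not shown. The one divergence visible in the text, Grade 3 against Grade 4 for transaminitis, stays inside the Grade 3-4 criterion of the general DLT list.

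The practical reach of that divergence is also limited. If the liver event were managed as immune-related hepatitis, Appendix 8 discontinues FPT155 at Grade 3 as well as Grade 4. Section 4.1.1.2 reports no DLT and no CRS through 560 mg, so no past decision is called into question.

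**Conclusion.** The dexamethasone line needs correcting. As printed it supports amounts 3.5-fold apart at 70 kg, and 2.5- to 4.5-fold apart over the assumed 50 to 90 kg. This rests on reading both amounts as per-dose figures, as the line is written. Two other readings reduce or remove the gap, but the text supports neither explicitly. It is a patient-safety matter because it concerns a rescue instruction; the review takes no position on the intended dose.

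The grading point is a cross-reference gap and does not show that the CRS scale is wrong. CTCAE 4.03 is set for adverse events with no stated exception, a CRS-specific scale exists by design, and the documents leave open which grade governs DLT calls, the Grade 3 and Grade 4 rows of Table 9, and SAP tabulation. No effect on the dose-escalation count has been demonstrated.

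**What to change.** 1. In footnote 2 of Table 16, reconcile the two dexamethasone figures and state in words how they relate, including whether each is per dose or per day. The sponsor should settle this against its source and with its clinical team.
2. State once, for example in 8.4, which CRS grade is recorded and used for DLT calls, dose modification and tabulation. Bring 4.1.1.3, Table 9, protocol Table 12 and SAP 6.3.1.2 into line with it. In doing so, reconcile Table 16's treatment of grade 4 transaminitis with the Grade 3 and Grade 4 rows of Table 9.

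The cost is one footnote and a sentence or cross-reference at each of the five places named, with no new data, visits or analyses. The protocol changes need the usual ethics approval under 10.1.3 and can go into one amendment. Item 1 is the one that should not wait.
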